8.2 Analysis Plan of Year 2 Component D

HAI antibody titers will be compared between groups receiving the mRNA COVID-19 and cclIV4 influenza vaccines concomitantly or sequentially for each of the four influenza vaccine strains contained in the respective vaccines for that season as well as circulating influenza viruses and SARS-CoV-2 variants. Specifically, we will assess the following objectives:

Primary Objective 1a: Compare the proportion of participants in each vaccination group with a seroprotective HAI titer ($\geq 1:40$) pre- and post-cclIV4 immunization for each cclIV4 antigen. These proportions will be compared between vaccination groups using an exact Mantel-Haenszel statistic.

Primary Objective 1b: Compare the proportion of participants in each vaccination group achieving seroconversion following cclIV4 (an HAI titer $\geq 1:40$ following cclIV4 immunization if the baseline titer is $< 1:10$ or a four-fold rise in HAI titer if the baseline titer is $> 1:10$) for each cclIV4 antigen. These proportions will be compared between vaccination groups using an exact Mantel-Haenszel statistic.

Primary Objective 1c: Compare the GMT for each cclIV4 antigen and circulating influenza viruses pre- and post-cclIV4 immunization in each vaccination group. GMT will be compared between vaccination groups using a regression model.

Primary Objective 1d: Compare the GMFR in HAI titer for each vaccination group. GMFR will be compared between vaccination groups using a mixed effects regression model with a random intercept.

Exploratory objectives will be assessed using exact Mantel-Haenszel statistics to compare proportions between vaccination groups, regression models to compare GMT, and mixed effects regression models to compare GMFR. Tables will be provided summarizing counts and proportions for categorical outcomes or summary statistics and confidence intervals for

continuous outcomes. The statistical analysis of each exploratory objective will be fully described in the statistical analysis plan (SAP).

HAI titers will be log transformed prior to analysis and back transformed to estimate GMT and GMFR. The same analysis plan for HAI titers will be repeated for MN titers.

Data analysis will be performed using SAS version 9.4 software (SAS Institute Inc., Cary, NC) or R software (R Core Team, Vienna, Austria).

REFERENCES

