### 3 STUDY ENDPOINTS

#### 3.1 Primary

- i. Proportion of participants in each vaccination group with a seroprotective HAI (in a subset of samples) titer ( $\geq 1:40$ ) pre- and post-cclIV4 immunization for each 2023-24 influenza vaccine antigen
- ii. Proportion of participants in each vaccination group achieving HAI seroconversion (a titer  $\geq 1:40$  following cclIV4 if the baseline titer is  $< 1:10$  or a four-fold rise in titer if the baseline titer is  $> 1:10$ ) following cclIV4 vaccination for each 2023-24 influenza vaccine antigen
- iii. HAI GMT for each 2023-24 influenza vaccine antigen pre- and post-cclIV4 in each vaccination group
- iv. GMFR in HAI titers for each 2023-24 influenza vaccine antigen in each vaccination group

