## 9 ANALYSIS OF STUDY OBJECTIVES

### 9.1 Primary Objective

The primary objective will be analyzed using the immunogenicity population. All endpoints will be assessed with two-sided tests and alpha set to 0.05.

*Endpoint i:*

The proportion of participants with a seroprotective HAI before and 28-42 days after immunization will be compared between group i (concomitant administration) and ii (influenza administered first), using the following null ( $H_0$ ) and alternative ( $H_1$ ) hypotheses:

$H_0$ : Simultaneous group – Sequential group = 0

$$H_0: \pi_1 - \pi_2 = 0$$

$$H_1: \pi_1 - \pi_2 \neq 0$$

where  $\pi$  is the seroprotective rate.

P values and confidence intervals for the geometric mean titer ratio will be estimated using a logistic regression adjusted for site.

*Endpoint ii:*

The proportion of participants achieving seroconversion will be compared between group i (concomitant administration) and ii (influenza administered first), using the following null ( $H_0$ ) and alternative ( $H_1$ ) hypotheses:

$H_0$ : Simultaneous group – Sequential group = 0

$$H_0: \pi_1 - \pi_2 = 0$$

$$H_1: \pi_1 - \pi_2 \neq 0$$

where  $\pi$  is the seroconversion rate.

P values and confidence intervals for the geometric mean titer ratio will be estimated using a logistic regression adjusted for site.

*Endpoint iii:*

GMTs before and 28-42 days after immunization will be compared between group i (concomitant administration) and ii (influenza administered first), using the following null ( $H_0$ ) and alternative ( $H_1$ ) hypotheses:

$$H_0: \mu_1 / \mu_2 = 1$$

$$H_1: \mu_1 / \mu_2 \neq 1$$

where  $\mu$  is the geometric mean titer.

P values and confidence intervals for the geometric mean titer ratio will be estimated using a generalized estimating equation linear regression accounting for site clustering.

*Endpoint iv:*

Geometric mean fold rise will be compared between group i (concomitant administration) and ii (influenza administered first), using the following null ( $H_0$ ) and alternative ( $H_1$ ) hypotheses:

$$H_0: \mu_1 / \mu_2 = 1$$

$$H_1: \mu_1 / \mu_2 \neq 1$$

where  $\mu$  is the geometric mean fold rise.

P values and confidence intervals for the geometric mean titer ratio will be estimated using a linear regression adjusted for site.

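### SAP 9.1 puts pre-vaccination HAI values under the primary hypothesis tests: on the natural reading, 8 of 24 primary tests use blood drawn before any study vaccine

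*SAP*

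**What the plan says.** SAP 9.1 gives explicit null and alternative hypotheses for four HAI endpoints, comparing group i (both vaccines together) with group ii (influenza vaccine first). The general rule is "All endpoints will be assessed with two-sided tests and alpha set to 0.05".

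Two endpoints name two time points each:

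- Endpoint i, on seroprotection: "The proportion of participants with a seroprotective HAI before and 28-42 days after immunization will be compared between group i (concomitant administration) and ii".
- Endpoint iii, on titres: "GMTs before and 28-42 days after immunization will be compared between group i (concomitant administration) and ii (influenza administered first), using the following null" hypothesis and its alternative.

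The other two name no separate pre-vaccination comparison:

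- Endpoint ii, on seroconversion: "The proportion of participants achieving seroconversion will be compared between group i (concomitant administration) and ii (influenza administered first").
- Endpoint iv, on fold rise: "Geometric mean fold rise will be compared between group i (concomitant administration) and ii (influenza administered first").

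SAP 3.1 repeats the endpoints by strain, for example "HAI GMT for each 2023-24 influenza vaccine antigen pre- and post-cclIV4 in each vaccination group". Protocol 8.2 counts four vaccine strains. Its objectives 1a and 1c also compare vaccination groups both before and after influenza vaccination. For 1a, once both time points have been named, the text continues: "These proportions will be compared between vaccination groups using an exact Mantel-Haenszel statistic".

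Neither document labels the pre-vaccination comparison as descriptive, names the post-vaccination comparison as the only test, or states a multiplicity adjustment.

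**The concern.** Groups i and ii both receive influenza vaccine at Visit 1. Protocol 5.1 has the Visit 1 blood drawn before vaccination, and the Visit 1 procedure list in Protocol 5.4.1 places the draw ahead of randomisation. For this contrast, then, the pre-vaccination sample precedes every study vaccine, and the schedule cannot have changed the titre in it.

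A test on that sample does not address the trial's question. If it gives P<0.05, the trial has a nominally significant primary result that says nothing about giving the vaccines together or apart. It also enlarges a family of primary tests that already has no error control. The SAP handles other baseline variables differently: section 8.2 summarises demographics by group and plans no tests.

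**Working it through.** **Inputs from the documents**

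- Two-sided alpha 0.05 for every primary endpoint (SAP 9.1).
- Endpoints with a pre-vaccination comparison: i and iii, so 2 (SAP 9.1).
- Endpoints with a post-vaccination comparison: i to iv, so 4 (SAP 9.1).
- Vaccine antigens: 4 (Protocol 8.2).
- Planned group sizes, i and ii: adults 300 and 150, children 100 and 50 (Protocol summary). All ages: 300 + 100 = 400 and 150 + 50 = 200.

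The plan gives no test count, familywise error rate or power calculation to reproduce.

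**Test count** (separate tests per time point, one pooled analysis per antigen)

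- Pre-vaccination: 2 x 4 = 8.
- Post-vaccination: 4 x 4 = 16.
- Total: 8 + 16 = 24, so 8/24 = one third are baseline tests.

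**False positives among the 8 baseline tests**

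- Expected number: 8 x 0.05 = 0.40.
- At least one, if independent: 1 - 0.95^8 = 33.7%.
- Bonferroni upper bound: 8 x 0.05 = 40%.

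**Allowing for correlation.** Endpoint i dichotomises the titre that endpoint iii averages, and strains may be correlated within a participant, so the tests are not independent. A null simulation used 4,000 trials per setting, with a t-test on log2 titres and a pooled z-test on titre at or above 1:40, both without a site term. The following inputs are assumptions, not figures from the documents: log2 SD 2, GMT about 30 before rounding to dilution steps, and between-strain correlation 0 to 0.6.

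| Group i vs ii | Correlation 0 | 0.3 | 0.6 |
|---|---|---|---|
| 300 vs 150 | 28.0% | 25.7% | 22.7% |
| 400 vs 200 | 28.0% | 26.7% | 22.8% |

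The chance of at least one baseline P<0.05 is therefore about 23-28% under these assumptions. The mean number of such results was 0.40 to 0.42 per trial, close to the expected 0.40.

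**Effect of removing the 8 tests** (global null; probabilities assume independence)

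- Tests: 24 to 16.
- Expected false positives: 24 x 0.05 = 1.2 to 16 x 0.05 = 0.8.
- At least one false positive: 1 - 0.95^24 = 70.8% to 1 - 0.95^16 = 56.0%.

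**The case against.** The best defence has four parts.

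**Baseline reporting belongs to the objective.** SAP 2.1 sets out to determine baseline as well as post-vaccination titres, and neither document has a success rule triggered by a single P value. Both statements are true. A table by arm meets that objective without a test, however, and the lack of a success rule does not make a baseline P value interpretable.

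**A baseline contrast has diagnostic value.** SAP 6.3 selects the Influenza Immunogenicity Population after randomisation, requiring both vaccines, no influenza or SARS-CoV-2 infection between Visits 1 and 2, and visits within window. The schedule can affect who meets these conditions: group ii must return for its second vaccine and has had no study COVID-19 vaccine during the interval. This stands. A reader might infer that a baseline difference can never have anything to do with the schedule, and that is too strong. The schedule cannot alter the Visit 1 titre, but it can alter who is retained. A descriptive table serves this check.

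**Much of the harm is multiplicity.** Also true. The 23-28% describes the baseline subset alone, and removing it leaves 16 unadjusted tests.

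**The Protocol is less specific than the SAP.** The Mantel-Haenszel sentence names no time point itself, and Protocol 8.2 does not confine the comparison to groups i and ii. In group iii the sample just before influenza vaccine is Visit 2, after COVID-19 vaccination, so the argument does not extend to it.

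A reader might also infer that the treatment effect is diluted, because the hypotheses carry no visit index and one model could hold both visits under a single group term. The documents do not support this. SAP 9.1 names only site adjustment or site clustering, with no visit term and no repeated-measures term for participant. The pooled model would also exclude the eight separate tests, so the two harms cannot be added together.

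**Conclusion.** The point holds for group i versus group ii in SAP 9.1. As written, endpoints i and iii place formal primary tests on samples that precede all study vaccination: 8 of 24 tests if time points are tested separately and each antigen has one pooled analysis. The SAP does not state that count, but its named models make this the natural reading. A significant result among the 8 could come only from chance or differential exclusion after randomisation.

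The chance of at least one is 33.7% under independence. The 23-28% range depends on an assumed titre distribution and correlation, and should be read as an order of magnitude. The post-vaccination comparisons remain unbiased by these tests. This is worth correcting because the change is simple, but it does not threaten the trial's main estimates.

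**What to change.** In SAP 9.1, limit the hypotheses and P values for endpoints i and iii to the 28-42-day sample. State that Visit 1 seroprotection and GMT will be tabulated by arm and antigen without a test, and that the table also serves to check for differential exclusion from the Influenza Immunogenicity Population. Align Protocol 8.2 objectives 1a and 1c for the group i versus ii contrast only. Any comparison involving group iii needs its own statement of which sample counts as pre-vaccination.

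SAP 9.2 reuses the primary methods for the MN, SARS-CoV-2 and circulating-virus serology, so check there, contrast by contrast, whether the same clarification applies.

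The cost is a wording amendment to both documents and fewer tests to program. No new data are needed and baseline values stay visible. Multiplicity across the remaining 16 tests must be settled separately.

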5.3.1	Participant Inclusion Criteria	23
5.3.2	Participant Exclusion Criteria	23
5.3.3	Temporary Delay Criteria (Visits 1 and 2)	24
5.3.4	Recruitment	25
5.3.5	Enrollment	26
5.3.6	Participant Withdrawal	27
5.4	STUDY SCHEDULE, PROCEDURES, & EVALUATIONS.....	27
5.4.1	Schedule of events and data collection	27
5.4.2	Randomization	32
5.4.3	Deviation from Protocol	33
5.5	DATA COLLECTION.....	33
5.5.1	Participant Demographics and Vaccine History	33
5.5.2	Follow-up Surveillance for Vaccine Reactogenicity and Safety and Self-Reported ARI or Change in Health Status Resulting in Hospitalization	33
5.5.3	Study Product Supply, Storage, and Administration	34
5.5.4	Biospecimens Collection & Handling	35
5.6	VACCINE SAFETY AND REACTOGENICITY.....	36
5.7	MEDICAL RECORD EXTRACTION.....	36

[figure not shown]
5.7.1	Prior Vaccination	36
5.7.2	Prior Lab-Confirmed Illness	37
6	HUMAN SUBJECTS PROTECTIONS	37
6.1	INSTITUTIONAL REVIEW BOARD REVIEW.....	37
6.2	PARTICIPANT CONFIDENTIALITY	38
6.3	RISKS AND BENEFITS TO PARTICIPANTS.....	39
6.4	RETURN OF RESULTS	41
6.5	COMPENSATION.....	42
7	DATA MANAGEMENT, TRANSFER, AND SECURITY	42
7.1	DATA MANAGEMENT AND TRANSFER.....	42
7.2	DATA SECURITY.....	43
8	STATISTICAL ANALYSIS	44
8.1	STUDY POPULATIONS.....	44
8.2	ANALYSIS PLAN OF YEAR 2 COMPONENT D.....	44
	REFERENCES.....	46
	LAB APPENDICES	47
	LAB APPENDIX A: RESPIRATORY SPECIMEN TESTING FOR INFLUENZA.....	48
	LAB APPENDIX B: HUMAN SERA COLLECTION GUIDELINES FOR INFLUENZA SEROLOGY.....	49
	LAB APPENDIX C: PERIPHERAL BLOOD MONONUCLEAR CELLS	50

[figure not shown]
PROTOCOL SUMMARY

Title:	Randomized study of the immunogenicity and duration of antibody response against circulating SARS-CoV-2 variant and influenza viruses following concomitant versus sequential administration of mRNA COVID-19 vaccine and quadrivalent cell culture-based influenza vaccine among children and adults
Phase:	Phase IV
Population:	600 persons aged 18-64 years and 200 children aged 6-11 years for whom a single dose of 2023-24 influenza vaccine and a single dose of mRNA COVID-19 vaccine is indicated as recommended by ACIP
Clinical Sites:	Four study sites: Arizona State University Tempe; University Hospitals of Cleveland; Washington University St. Louis; University of Pittsburgh
Coordinating Site:	Duke University

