Study Duration:	12 months total Enrollment: Aug — Oct 2023 Vaccination: Aug — Nov 2023 Blood draws: Aug 2023 — May 2024 Active surveillance for illness: Aug 2023 — May 2024 Laboratory testing: Nov 2023 — Jul 2024
Participant Duration and Number of Participants:	
 • Up to 10 months (Aug 2023 — May 2024) • 800 total participants (600 aged 18-64 years, 200 aged 6-11 years) at 4 sites (only two sites will enroll children aged 6-11 years)
Randomization:	Adults aged 18-64 years, 2:1:1 permuted block randomization 
 i. Concomitant cclIV4 + COVID-19 mRNA (day 0) [n = 300] ii. Sequential cclIV4 (day 0), COVID-19 mRNA (day 28) [n = 150] iii. Sequential COVID-19 mRNA (day 0), cclIV4 (day 28) [n = 150]

	
Children aged 6-11 years, 2:1:1 permuted block randomization
 
 i. Concomitant ccIV4 + Moderna COVID-19 mRNA (day 0) [n = 100] ii. Sequential ccIV4 (day 0), Moderna COVID-19 mRNA (day 28) [n = 50] iii. Sequential Moderna COVID-19 mRNA (day 0), ccIV4 (day 28) [n = 50]

Description of Study Procedures:
	
This study is a randomized immunogenicity study in an enrolled cohort with active surveillance for acute respiratory illness (ARI). During this study, participants will be randomly assigned to receive an approved quadrivalent influenza vaccine (Flucelvax [ccIV4]) and mRNA COVID-19 vaccine (Moderna) either concomitantly (given in contralateral arms) or sequentially (28 days apart).
 
Blood samples from participants will be collected for measurement of biomarkers of immune response at baseline (visit 1; day 0), post-vaccination 1 (visit 2; day 28), post-vaccination 2 (visit 3; day 56), and post-season (visit 4; day 180). Serum and peripheral blood mononuclear cells (PBMC) and plasma (target to collect PBMC and plasma samples at every visit from a subset of approximately 250 participants; 200 adults and 50 children) samples will be isolated from whole blood and tested for biomarkers of vaccine immunogenicity, and duration of antibody responses.

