5.3.4.4 Arizona State University, Tempe

Arizona State University will recruit local student and faculty population through study flyers. Valleywise Health will recruit employees via study flyers and the intranet. Phoenix Children's Hospital will approach and recruit patients presenting for seasonal influenza vaccination or mRNA COVID-19 vaccination and via study flyers.

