## 4.3 Randomization

Permuted block randomization stratified by age group (children aged 6-11 years and adults aged 18-64 years) and site will be used at each site to ensure even allocation to each study arm. At each site, participants will be randomized 2:1:1 to receive: (i) concomitant administration of a mRNA COVID-19 vaccine and a quadrivalent influenza vaccine (cclIV4), (ii) sequential administration of a quadrivalent influenza vaccine (cclIV4) at Visit 1 (day 0) and a mRNA COVID-19 vaccine at Visit 2 (day 28), and (iii) sequential administration of a mRNA COVID-19 vaccine at Visit 1 (day 0) and a quadrivalent influenza vaccine (cclIV4) at Visit 2 (day 28).

The project statistician will generate the randomization schemes which will be uploaded to REDCap. The randomization schedule will not be available to the study staff, so the next randomization allocation will not be known before randomization occurs. Following confirmation of study eligibility criteria during Visit 1, participant randomization will be through REDCap with treatment allocation recorded on the case report form (CRF).

In the event that REDCap is unavailable, participants will be manually randomized through the use of sealed envelopes with randomization allocations enclosed. The project statistician will prepare envelopes that will use the same randomization strategy as the primary scheme embedded in REDCap. When an unblinded team member is informed of the age group, they will pull the next envelope in order. To capture the allocation per subject, a separate form in REDCap will be used by the unblinded study personnel to add the assignment. Sites will need to keep a log capturing these instances. The next available sequential study-number will be assigned to each enrolled participant upon study-entry.

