## 7.1 Multicenter Studies

There are 7 sites participating in the study. Data will be pooled across investigational sites for analysis purposes. A fixed site effect will be included in all analyses of the primary objective.

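### SAP 9.1 endpoint iii (GMT) uses a site-clustered GEE with no stated standard error or reference distribution; if run with an uncorrected sandwich and z on 4 or 7 sites, it would reject about 12–19% under the null, not 5%

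*SAP*

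**What the plan says.** SAP 9.1 compares group i (both vaccines together) with group ii (influenza vaccine first) on four primary endpoints, and sets the level for all of them: "All endpoints will be assessed with two-sided tests and alpha set to 0.05".

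- Endpoints i and ii (seroprotection, seroconversion): logistic regression with site adjustment.
- Endpoint iv (GMFR): linear regression with site adjustment.
- Endpoint iii (GMT, before and 28–42 days after vaccination): the ratio is to be "estimated using a generalized estimating equation linear regression accounting for site clustering".

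SAP 7.1 gives a general rule: "A fixed site effect will be included in all analyses of the primary objective". SAP 4.3 describes individual randomisation within strata: "Permuted block randomization stratified by age group (children aged 6-11 years and adults aged 18-64 years) and site will be used at each site".

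The number of sites differs between the documents. SAP 7.1 says "There are 7 sites participating in the study"; the Protocol Summary says "Four study sites" and adds that "only two sites will enroll children aged 6-11 years".

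Neither document gives the GEE's working correlation, standard error, small-sample correction or reference distribution. SAP section 7 names only the software (SAS or R), and protocol 8.2 asks only for a regression model for GMT. SAP 9.2 (Serology) applies the primary methods to the MN, SARS-CoV-2 and circulating-virus objectives.

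**The concern.** A GEE clustered by site is very often run with the empirical (sandwich) standard error and a normal reference. That combination relies on having many clusters. With 4 or 7, the uncorrected sandwich is biased downwards and z ignores how poorly the variance is estimated, so the test rejects too often and intervals are too narrow.

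An analyst could follow the SAP's wording in this way and report a chance GMT difference as an effect of co-administration. At stake are one of four primary endpoints, tested for each vaccine antigen, and the exploratory GMTs that borrow its method. Endpoints i, ii and iv are not affected.

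The design does not need site clustering for validity. Individuals are randomised within site, so the treatment contrast is a within-site contrast.

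**Working it through.** **Inputs from the documents.** Two-sided alpha 0.05 (SAP 9.1). Allocation 2:1:1, hence 2:1 for group i against group ii. Planned sizes from the Protocol Summary: 300 + 100 = 400 in group i and 150 + 50 = 200 in group ii. Sites: 7 (SAP 7.1) or 4 (Protocol Summary), with children at two.

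**Assumed.** Adults and children pooled (SAP 9.1 does not say); log2-titre SD 2; site SD 0.5; age difference 1; no site-by-treatment variation; all splits of participants across sites.

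**Step 1: the plan's own 5%.** Linear regression of log2 titre with fixed site effects and a t reference has type I error of exactly 5% under normal errors. Simulated with site and age group it gave 4.7–5.1% in every layout below.

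**Step 2: closed form for the uncorrected sandwich with z.** Take K equal sites with constant allocation within site. The GEE estimate is the mean of the K site differences d_k.

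- Uncorrected sandwich variance: Σ(d_k − d̄)² / K²
- Usual variance of a mean: Σ(d_k − d̄)² / [K(K−1)]
- Ratio of the first to the second: (K−1)/K

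The z test therefore rejects when |t on K−1 df| > 1.96·√((K−1)/K).

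- K = 7: threshold 1.96 × √(6/7) = 1.815; 2·P(t₆ > 1.815) = 12.0%
- K = 4: threshold 1.96 × √(3/4) = 1.697; 2·P(t₃ > 1.697) = 18.8%

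The titre SD cancels, so these two figures do not depend on it.

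**Step 3: simulation, 20,000 null trials per layout**, groups i and ii, 2:1 within each site-by-age stratum. The 7-equal layout has 392 and 196 participants; the others have 400 and 200.

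| Layout (assumed sizes) | Uncorrected sandwich, z | K/(K−1) sandwich, t on K−1 df | CR2, Satterthwaite df | Mean SE: sandwich, then site+age regression |
|---|---|---|---|---|
| 4 sites, children at two | 19.3% | 5.2% | 4.6% | 0.1360, 0.1731 |
| 7 near-equal for adults, children at two | 12.9% | 5.0–5.6% | 4.8% | 0.1512, 0.1732 |
| 7 equal, children at every site | 11.8% | 5.0% (closed form) | – | 0.1550, 0.1748 |
| 7 uneven, children at two | 16.1–16.4% | 8.0–8.2% | 3.8% | 0.1414, 0.1731 |

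The equal layout is a benchmark for the closed form only, because the protocol allows children at just two sites. A second set of uneven sizes gave 16–17%.

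**Step 4: do site terms in the GEE help?** No. At 4 sites the 19.3% is the same with site, site-plus-age or stratum indicators. With 7 equal sites and site indicators the rate stays at about 12–13%.

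**Step 5: other choices the SAP's silence allows.** A model-based exchangeable GEE gives 4.7% (4 sites) and 4.9–5.2% (7 sites). An uncorrected sandwich with t on K−1 df gives 7.0% (4) and 6.4% (7), so changing the reference alone is not quite enough.

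**Step 6: effect varying between sites** (SD 0.2 log2, mean zero, assumed), judged as a test of the average over a wider population of sites.

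| Method | 4 sites | 7 sites |
|---|---|---|
| Fixed-effect regression | 8.5–9.6% | 7.1–7.3% |
| Uncorrected sandwich, z | 19.8% | 12.7% |
| K/(K−1) sandwich, t on K−1 df | 5.3–5.8% | 5.2–5.5% (equal sizes) |

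**Step 7: site count.** Protocol 5.3.4.4 shows the Arizona site recruiting through three institutions, for example "Valleywise Health will recruit employees via study flyers and the intranet". Counting each separately gives 4 − 1 + 3 = 6, not 7. The documents do not settle the number.

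**The case against.** **The inflation is conditional.** No text specifies an uncorrected sandwich or a z reference. The same silence allows a model-based standard error, which holds about 5%. This stands. A reader might infer that the SAP plans a test with 12–19% error; it does not. It leaves open a choice that decides whether 0.05 holds.

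**Conflict with SAP 7.1.** A reader might infer an outright contradiction. But a GEE can carry site indicators, so 7.1 and 9.1 can be read together and the conflict is one of wording. Reading them together does not remove the problem, as step 4 shows.

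**Clustering can be defended.** It would also be too strong to call site clustering wrong under individual randomisation. If the effect varies between sites and inference to a wider population of sites is wanted, a corrected sandwich with t holds its level better than fixed-effect regression when sites are few but near equal (step 6). With uneven sites and the simple correction that advantage disappears: 8.7% against 8.5%. So a properly specified GEE is an equal remedy, not a second best.

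**Layouts.** All site sizes are assumed. The 7-equal layout does not fit the protocol, but the near-equal layout that does fit gives a slightly higher figure, so the benchmark does not exaggerate the problem.

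**Conclusion.** The point holds as under-specification of one primary analysis. Endpoint iii alone uses a site-clustered GEE, its standard error and reference distribution are not stated, and there are only 4 or 7 clusters. If, and only if, it is run with an uncorrected sandwich and z, type I error is about 12–13% (7 equal or near-equal sites), 16–17% (7 uneven) or 19% (4 sites), which is roughly 2.4 to 4 times the stated level.

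The equal-site figures follow in closed form and do not depend on the titre SD. The other figures rest on assumed site sizes and on pooling the age groups. Confidence is high in the omission and the arithmetic. The documents give no basis for saying how likely the inflating option is to be used.

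The SAP also does not say whether the pre- and post-vaccination GMTs have separate models. That should be stated, but no error rate is attached to it here.

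**What to change.** For endpoint iii, and for the MN, SARS-CoV-2 and circulating-virus GMTs that borrow its method, use the endpoint iv model. Regress log2 titre on group separately at each time point, with the fixed site effects that SAP 7.1 requires, a model-based or HC standard error and a t reference. Report 2^b as the GMT ratio with its 95% CI.

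**Separate small improvement.** Add age group, the other randomisation stratum. This goes beyond SAP 7.1 and endpoint iv, which name site only. Under the assumed age difference it narrows intervals by about 2% (at 4 sites, mean SE 0.1764 to 0.1731).

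**Equal alternative,** if a wider population of sites is the target: keep the GEE and pre-specify a small-sample-corrected sandwich with a t reference. K/(K−1) with K−1 df serves for 4 or near-equal sites; use CR2 with Satterthwaite df if sites are uneven. CR2 intervals are 56% (4 sites) or 24–47% (7 sites) wider than those from regression on site and age group.

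**Site count.** Reconcile 4 with 7, so that the site terms match those used in randomisation.

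**Cost.** A few lines of SAP text and code, and no new data. From the mean SEs above, regression intervals are wider than uncorrected-sandwich intervals by 27% at 4 sites (0.1731/0.1360), 13–15% at 7 equal or near-equal sites and 22% at 7 uneven sites. They are almost unchanged from a model-based GEE. Fixed-effect regression speaks to the trial's own sites; for a wider population of sites it would reject about 7–10% under the site variation assumed in step 6.
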